1 ABSTRACT

Cellular therapy holds great promise in medicine. This proposal will employ autologous fibroblasts in an attempt to help the more than 1.7 million (1 out of every 200) people in the US who have had limb amputations. While improvements in prosthetics have been made, their use is still dramatically limited by pain and skin-breakdown at the stump site. Our long-term goal is to permanently convert the skin at the stump site to **volar type (palmo-plantar)** skin. Volar epidermis is markedly thicker than skin at other locations and **uniquely** expresses Keratin 9 (KRT9) which makes it more friction- and irritant-resistant. We and others have shown that volar fibroblasts have the ability to increase epidermal thickness in 3-D and induce ectopic KRT9 **in non-volar keratinocytes** in both 2-D and 3-D co-cultures. (Given that KRT9 is a suprabasalar keratin, and unique to volar skin, it is an ideal read-out). Therefore our aim is a proof-of-concept demonstration

Hypothesis: Autologous volar fibroblasts have the capacity to induce ectopic volar gene expression such as KRT9 in human subjects. To investigate this, we intend to:

Phase One

1. Inject autologous volar and nonvolar fibroblasts in paired areas of the buttocks, or non-buttocks area. (All non-buttocks areas will exclude genitals, face, or at joints) Perform noninvasive imaging over a maximum period of 6 months to monitor for thickened epidermis/stratum corneum and longevity of effect. Also, if early thickening occurs, then we will remove injected skin area early in ½ of participants for #2.
2. Analyze epidermis by both histology and RT-PCR for features of volar phenotype (KRT9, epidermal thickness, stratum corneum thickness, presence of PAX9^{high}, LMX1b^{low}, EMX2^{low}, SHOX^{low} fibroblasts)

Phase Two

3. Identify optimal methods of delivery that will enhance skin reprogramming and improve conversion of non-volar to volar skin. We propose 2 testing methods with the goal of enhancing volar fibroblast stem cell engraftment: (a) We will investigate the efficacy of multiple, intermittent injections, while holding the total number of injected cells constant. (b) An additional approach is to lightly curette the skin at the injection sites to test if superficial wounding of the epidermis enhances volar fibroblast stem cell engraftment.

If successful, the results of this proposal will be a first to ectopically reprogram human skin identity.

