Through a seedling grant from DARPA we have verified that volar fibroblasts have the ability to induce KRT9 in cells which do not normally do so. We biopsied human volunteers, cultured either volar or non-volar fibroblasts, and added them to foreskin keratinocytes. We detected that just as in normal human skin (Figure 4), palm or sole fibroblasts could induce ectopic KRT 9 (Figure 5). Given that KRT9 is a suprabasal keratin found only in differentiated volar keratinocytes, this strongly supports their use in inducing ectopic volar skin in amputees.

To verify the accuracy of our assay, we have done extensive microarrays. We discovered a master regulatory gene which controls the volar phenotype—the homeobox gene LMX1b. If we knockdown LMX1b then we can now endow even non-volar cells with the ability to induce KRT9 (Figure 6). We have also verified KRT9 inductivity persists through passage 16 of fibroblasts, with one biopsy yielding more than 100 million fibroblasts in a month.

Besides these in 2-D in vitro assays, there is further proof for the inductive power of fibroblasts. In 3-D cultures human volar fibroblasts can make ectopic thickened epidermis and stratum corneum from foreskin keratinocytes (Fig 7). Similarly, Fig 3 demonstrates that non-volar keratinocytes are turned into volar keratinocytes when transplanted to volar fibroblasts. Also Yamaguchi et al demonstrated that human volar fibroblasts could also convert non-volar to volar keratinocytes in a SCID mouse model[2]. We ourselves have performed similar assays where we add mouse keratinocytes either alone or plus inductive fibroblasts and we can show that fibroblasts direct the development of hair growth. These results provide in vivo evidence on how fibroblasts can change epidermal function and control skin identity.

In the course of these studies we have enrolled 11 participants who have had sole/foot biopsies (NA_00033375). Of 11 biopsies, only a single one had a possible infection which was successfully treated with antibiotics. Otherwise there were no adverse events. Therefore we predict a similar safety profile for the currently proposed study.

Phase One - Proposed therapeutic outline:

1. Biopsy palmo/plantar skin at the sole of the foot and the scalp (or other area with suitable non-volar skin) (note higher KRT9 in native tissue in Fig 4 and KRT9 induction in Fig 5)
2. Expand autologous palmo/plantar fibroblasts

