A xenograft is in a chronic “wounded state” given the preparation that is required for the graft to “take.” This state is not equivalent to the scenario into which our cells are being transplanted.

PREPARATION

The fibroblasts are cultured, using standard methodologies, from a small punch biopsy that includes the epidermal and dermal layer taken from a volar (palm or sole) or a nonvolar skin site. During and after in vitro expansion, the fibroblasts are harvested and quality control tests are performed. Greater than 95% of the final suspension is composed of fibroblasts as most of the keratinocytes are removed in the initial stages of processing.

Once the final suspension reaches up to 37.5 million fibroblasts, the cell suspension is cryopreserved in freezing media containing human serum albumin, hetastarch and dimethyl sulfoxide (DMSO) (2.5% human serum albumin, 5% DMSO, 6% hetastarch in sterile saline) at a defined fibroblast cell concentration. Before clinical use, cells are thawed and then injected via an intradermal route into the autologous graft site within 24 hours. For Phase Two’s intermittent dosing, each dose will be frozen separately and thawed the day of injection. The transplant volume will contain no more than 37.5 million cells in 0.75 mL of freezing media.

DOSE SPECIFICS

Dosing of our therapy has also provided challenges. We chose 37 million cells based on a number of considerations, many from our investigations in optimizing hair follicle neogenesis using mouse cells. It is important to note that this value may require some optimization. Lower dosages may be used, up to 37.5 million cells. We also propose to administer multiple doses intermittently over 30 days (see Schema, page 4). In the assay that closely parallels this work, we try to convert tissue identity and create hair follicle structures from single cell slurries of both keratinocytes and fibroblasts. In these efforts, we discovered a continuously enhanced rate of hair follicle creation with a higher amount of fibroblasts and keratinocytes used[11]. In our present effort, we are not injecting keratinocytes but using the native keratinocytes that are present and extend for a much greater area than the injection area. Therefore, to optimize our efforts, we wish to try an adequate number of fibroblasts in a small area to maximize proximity of the fibroblasts to the superiorly oriented epidermis.

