9.2 ANALYSIS PLAN

The first method of analysis will happen during each participant's graft monitoring visits to determine whether they will be one of three "Early Graft Removal" subjects. Three epidermal thickness measurements will be calculated at each monitoring visit for each injection site. We will analyze this data to determine whether volar fibroblasts caused an increase in epidermal thickness. The means of determining whether an increase is statistically significant will be through a t-test statistical analysis of 3 independent readings from the three injection sites (no fibroblasts, non-volar fibroblasts, and volar fibroblasts). We will consider a p value less than 0.05 as significant. For a subject to be designated as an "early graft removal", he/she should have a statistically significantly elevated epidermal thickness in the volar injected site but not the non-volar or vehicle-only injected sites.

For statistical analysis at the conclusion of the study we will average multiple subject's values. We will perform a student's T-test comparing the values of epidermal thickness between at least 3 non-volar fibroblast injections and 3 volar fibroblast injection to determine a p value for a significant difference. We will consider a p value less than 0.05 as significant. We will do the same for KRT9 mRNA values. As more participants complete the study, we will repeat this calculation until our enrollment goal is met.

Power analysis: With a difference of mean assumed to be 2, standard deviation of all samples to be 0.5, alpha 0.06, power of 0.8 then a sample size of 3 participants will be sufficient and our goal will exceed this.

We will perform repetitive interim data analysis as each participant completes the final time point.

We will also calculate average areas of increased epidermal thickness.

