9.2.2 SECONDARY OUTCOME VARIABLES

Secondary outcome variables for this study will be 1) an increase in epidermal thickness as detected by optical coherence tomography in vivo, or by histology, and 2) an increase in KRT9 by RT-PCR, western or immunohistochemistry

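### KRT9 mRNA alone can support the conversion claim, yet volar keratinocytes carried over in the volar product could raise it at the volar site only; require KRT9 localised in the surface epidermis.

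*Combined protocol and SAP*

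**What the plan says.** **Why KRT9.** Section 1 (Abstract): "Given that KRT9 is a suprabasalar keratin, and unique to volar skin, it is an ideal read-out". The rationale has two parts, suprabasal position and specificity to volar skin. Section 3 (Background, Preliminary Studies) names the cell that makes it: "KRT9 is a suprabasal keratin found only in differentiated volar keratinocytes".

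**What is injected.** Section 8.1 (Preparation) says the fibroblasts are cultured "from a small punch biopsy that includes the epidermal and dermal layer taken from a volar (palm or sole) or a nonvolar skin site". On purity it says: "Greater than 95% of the final suspension is composed of fibroblasts as most of the keratinocytes are removed in the initial stages of processing". Section 6.2.1 refers release testing, including purity, to the IND, which is not part of these documents.

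**How KRT9 is tested.** Section 9.2 sets out a Student's t-test of epidermal thickness between volar and non-volar fibroblast injections at p < 0.05, then adds: "We will do the same for KRT9 mRNA values". Section 9.2.2 defines the secondary outcome as "an increase in KRT9 by RT-PCR, western or immunohistochemistry".

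**What tissue is available.** Appendix VII takes a 3-6 mm punch of each of the three injected sites and bisects it, one half into RNA-later and the other into paraformaldehyde. It describes no separation of epidermis from injected dermis, although Section 1 speaks of analysing epidermis. Sections 1 and 4.1.1 both plan histology as well as RT-PCR, and Section 4.1.1 has the laboratory staff blinded.

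**The concern.** The hypothesis is that volar fibroblasts make the participant's own non-volar keratinocytes express KRT9. An mRNA rise at the volar site supports this only if the injected product brought no KRT9-capable cells with it. The starting tissue contains such cells, and the documents say that most of them, not all, are removed.

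Neither comparator would expose the problem. The non-volar product would carry non-volar keratinocytes, which on the plan's own premise do not make KRT9. The vehicle carries no cells. Any carry-over effect therefore falls on the volar site alone and favours the hypothesis. Blinding, within-person pairing and more participants do not remove it.

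At stake is the reading of one secondary outcome, but an important one. Section 1 says that success would be the first ectopic reprogramming of human skin identity, and Section 4.4.2 uses induction of volar genes such as KRT9 in defining treatment failure. As written, RT-PCR alone could meet the KRT9 outcome.

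**Working it through.** The purity figure is a product description, so the plan has no calculation to reproduce. What can be checked is the ceiling it implies, and whether anything in the plan would separate carry-over from conversion.

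**1. Ceiling on non-fibroblasts (Section 8.1).** Purity is above 95%, so non-fibroblasts are below 5%. Section 8.1 sets the upper limit per transplant: "The transplant volume will contain no more than 37.5 million cells in 0.75 mL of freezing media".
- 0.05 × 37.5 million = 1.875 million, so under 1.9 million.
- Sections 5.2.4 and 8.1 do not give the same cell number and must be reconciled. For the 30-40 million in Section 5.2.4 the ceiling is 0.05 × 30 = 1.5 to 0.05 × 40 = 2.0 million.

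This bounds all non-fibroblasts. The documents do not say what share are keratinocytes.

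**2. Scale against native keratinocytes (Section 8.1, Dose Specifics).** The plan counts 800 × 800 = 640,000 basal cells in a 4 mm punch and about four layers. That product is 2.56 million, while the text prints 2.88 million; the two must be reconciled, but the point does not depend on which is used.
- 1.875 / 2.56 = 73%; 1.875 / 2.88 = 65%.
- Appendix VII allows punches up to 6 mm. By the same arithmetic, 1,200 × 1,200 × 4 = 5.76 million, and 1.875 / 5.76 = 33%.

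These are ceilings. They need purity at the limit, every non-fibroblast to be a keratinocyte, and every one to survive to excision.

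**3. Allowing for loss (assumed range).** The documents give neither the keratinocyte share nor persistence. Let f be their product, so that cells remaining = 1.875 million × f:

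| f (assumed) | Cells remaining | Share of 2.56 million |
|---|---|---|
| 10% | 187,500 | 7.3% |
| 1% | 18,750 | 0.73% |
| 0.1% | 1,875 | 0.07% |

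Nothing in the documents favours one row, and f could be lower still. No KRT9 expression level per cell or background level is given, so cell numbers cannot be turned into an mRNA difference.

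**4. What a shift would do to the test (illustration only).** Section 9.2 assumes a standard deviation of 0.5. Suppose carry-over alone moved the volar mean by an assumed 0.5, 1 or 2 of the same units. A two-sided, unpaired t-test at 0.05 with 3 per group would then be significant 16%, 46% or 95% of the time. At a shift of 0.5 the figure rises from 16% with 3 per group to 56% with 10 and 87% with 20. The shifts are not estimates. They show only that a one-sided bias is not diluted by enrolling more participants.

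**5. Would anything in the plan separate the two explanations?**
- *Comparator sites:* no, for the reasons given under the concern.
- *Genotype:* no. The cells are autologous.
- *mRNA from the half-punch:* no. Injected and native cells are in the same tissue, and no separation step is described.
- *Histology of the fixed half:* in part. It shows whether KRT9 lies suprabasally in continuous surface epidermis or in nests in the dermis. But Section 9.2 gives it no role in the KRT9 test, and Section 9.2.2 makes immunohistochemistry optional.

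**The case against.** Four objections carry weight.

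*Carry-over may be trivial.* Keratinocytes are removed at the start of processing. Any that remain must then survive expansion (up to 40 days, Section 4.4.1), freezing and thawing, and persist from injection near day 30 to scheduled excision at day 182: 182 − 30 = 152 days, about five months. This stands. It limits the size of the concern, although the documents do not show that the effect is nil.

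*Localisation is already planned.* Sections 1 and 4.1.1 and Appendix VII provide for blinded histology and fixed tissue, and the suprabasal half of the KRT9 rationale is what histology can use. This also stands. The gap is narrower than missing data: no rule makes the conversion claim depend on that reading.

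*The IND may hold a tighter limit.* It may, and citing a keratinocyte limit would go far towards answering the point. None is stated here.

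*KRT9 is a secondary outcome in a feasibility study.* True. The primary outcome (Section 9.2.1) is tolerability, and epidermal thickness is a separate secondary outcome.

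A reader might go further and infer that carried-over keratinocytes could number well over half of the native ones, or that even a trace would give a large fold change. The documents support neither. The first treats a ceiling on all non-fibroblasts as a count of surviving keratinocytes. The second needs expression and background figures that are not given.

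**Conclusion.** The concern holds as a gap in interpretation. With the present wording a KRT9 conversion claim could rest on mRNA alone, and the design would not distinguish conversion from volar keratinocyte carry-over. The direction, if there is any effect, favours the hypothesis. The size is unknown and may be negligible; the only bound available is under 1.9 million non-fibroblasts of any kind per 37.5 million cells.

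The conclusion rests on two assumptions: that some volar keratinocytes could remain in the product, which the wording on purity leaves open, and that some could persist and express KRT9 at excision, which the documents neither show nor exclude. It would be wrong to infer that a positive mRNA result would be an artefact, or that KRT9 is an unsuitable marker. Neither follows. The tolerability outcome is untouched.

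**What to change.** **Sections 9.2 and 9.2.2.** Replace the *or* between assays with a rule. A claim of KRT9 conversion requires blinded immunohistochemistry on the paraformaldehyde half showing suprabasal KRT9 in the continuous surface epidermis over the volar site. KRT9-positive nests in the dermis are reported separately and do not count. KRT9 mRNA is reported as supportive. Report the reading for all three sites of each participant.

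**State the limit.** Say that localisation reduces the ambiguity but does not prove which cells made the KRT9, because the graft is autologous.

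**Blinding.** Appendix VII labels the excision tubes with vehicle, volar or non-volar identity, which conflicts with the numbered sites of Section 4.1.1. Use coded labels so that the reading is blind.

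**Product purity.** Cite the keratinocyte limit in the IND if there is one. Testing surplus released product for KRT9 and keratinocyte markers is a useful option, but the documents do not establish that surplus exists. A KRT9-negative product would not exclude undifferentiated volar keratinocytes, since Section 3 places KRT9 only in differentiated ones.

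**Cost.** Wording changes, coded labels and consistent use of an assay the plan already lists on tissue it already collects, with no extra visit or biopsy. The downside is that mRNA alone can no longer carry the claim.

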2 PRIMARY OBJECTIVE

1. To determine the safety and tolerability of the use autologous volar fibroblasts to reprogram non-volar to KRT9-expressing volar epidermis in human participants.

SECONDARY OBJECTIVES

1. To measure non-invasively for epidermal thickening in sites of injection of volar fibroblasts compared to both non-volar fibroblast injection and vehicle only injection
2. To measure for molecular changes in excised injected skin (for example increases in KRT9).
3. To describe persistence of epidermal thickening in sites of injection of volar fibroblasts over time.
4. To evaluate the safety and efficacy of an intermittent, serial dosing regimen of the autologous volar fibroblasts.
5. To evaluate the efficacy of superficial wounding with a curette at the injection sites.

3 BACKGROUND

[figure not shown]

Figure 1: Properties of Volar versus Non-Volar Skin. Note **Keratin 9** expression is limited to thick volar skin.

(Adapted from Rinn et al[1])

Solution: Convert stump skin to weight-bearing volar (i.e. palmoplantar) skin

The goal of this proposal is to make the placement of a prosthetic at a stump site analogous to the placement of a shoe on a foot, for example. We hope to achieve the rarity of skin break-down at the soles of our feet for stump sites in amputation victims. Therefore we propose to convert stump

skin to volar type skin with its attendant friction-resistant, irritant-resistant and weight bearing properties.

Properties of Volar Skin (Figure 1)

Volar skin, found at our palms and soles, has many distinguishing features adapted for their location as frequent points of interface with our environment. The primary feature of volar skin is the thick stratum corneum—the very top layer of skin which consists of dead keratinocytes which are cross-linked to form a strong water-impermeable layer. This stratum corneum is approximately 10 times as thick as in other parts of the skin. The thickness of this layer allows for more even distribution of weight across volar skin, resistance to friction, resistance to injury and impermeability to irritants and allergens.

These physical differences are reflected in different proteins which are expressed in volar skin (see Preliminary Studies). The most well studied one is Keratin 9. This structural molecule is unique to volar skin and provides tensile strength to cells (Figure 1).

Fibroblasts: Candidate Therapy to Convert Non-Volar to Volar Skin

The skin is made of two parts, the top epidermis and the bottom dermis. The predominant cell in the epidermis is the keratinocyte. The predominant cell in the dermis is the fibroblast. Fibroblasts have important functions in controlling tissue identity. Evidence for this comes from both animal studies and human studies.

The primary innovation of this investigation is to clinically apply established concepts in developmental biology of the mesenchymal (dermal fibroblast) control of epithelial (keratinocyte) function. Early experiments swapping chicken and duck epithelium and mesenchyme established that mesenchyme controls epidermal identity[3]. We hope to translate this fundamental concept to help improve the quality of life for amputation victims.

Human studies demonstrate similar results. Scalp dermal fibroblasts create long hairs if transplanted to the arm[4]. Part of the mechanism of this effect is that fibroblasts can “remember” their origin position in the body. When human dermal fibroblasts are removed from different areas of the skin, and their gene expression is measured, fibroblasts maintain expression of specific genes which reflect the location of origin of the fibroblasts: Hox or homeobox genes [5-8]. Fibroblasts retained their Hox signatures even after 35 cell doublings in cell culture[9]. The Hox genes control tissue identity as shown most plainly in the case of drosophila (Figure 2). In summary, dermal fibroblasts control skin identity, probably through expression of Hox genes.

Volar Fibroblasts Control Volar Keratinocyte Gene Expression

Volar skin has thickened stratum corneum and epidermis. Early experiments using human cells by Yagamuchi et al confirmed that dermal fibroblasts control KRT9 expression. In this experiment, human plantar fibroblasts can convert trunk keratinocytes into a thickened KRT9 positive epidermis when transplanted to SCID mice[2]. Also, when human non-volar epidermis is transplanted to palm dermis, the epidermis thickens and expresses KRT9, indicating that palmar dermis directs epidermal identity (Figure 3). The specific innovation of this research is to establish the reciprocal concept: human fibroblasts are capable of inducing KRT9 and can induce ectopic volar skin in human participants.

Yagamuchi extended this work to demonstrate that DKK-1 is elevated in volar fibroblasts and has the ability itself to increase epidermal thickness and decrease pigmentation in volar epidermis[10]. Similarly Rinn et al demonstrated that the distal homeobox A13 (HOXA13) is necessary for KRT9 induction and induces Wnt5a which itself also can stimulate KRT9 expression [8].

In conclusion, in the search for therapies to induce ectopic volar skin, we choose to focus on the fibroblasts themselves—which maintain their identity in culture[5], and have a lower regulatory hurdle for use—rather than any particular signaling factor.

Preliminary Studies

Through a seedling grant from DARPA we have verified that volar fibroblasts have the ability to induce KRT9 in cells which do not normally do so. We biopsied human volunteers, cultured either volar or non-volar fibroblasts, and added them to foreskin keratinocytes. We detected that just as in normal human skin (Figure 4), palm or sole fibroblasts could induce ectopic KRT 9 (Figure 5). Given that KRT9 is a suprabasal keratin found only in differentiated volar keratinocytes, this strongly supports their use in inducing ectopic volar skin in amputees.

To verify the accuracy of our assay, we have done extensive microarrays. We discovered a master regulatory gene which controls the volar phenotype—the homeobox gene LMX1b. If we knockdown LMX1b then we can now endow even non-volar cells with the ability to induce KRT9 (Figure 6). We have also verified KRT9 inductivity persists through passage 16 of fibroblasts, with one biopsy yielding more than 100 million fibroblasts in a month.

Besides these in 2-D in vitro assays, there is further proof for the inductive power of fibroblasts. In 3-D cultures human volar fibroblasts can make ectopic thickened epidermis and stratum corneum from foreskin keratinocytes (Fig 7). Similarly, Fig 3 demonstrates that non-volar keratinocytes are turned into volar keratinocytes when transplanted to volar fibroblasts. Also Yamaguchi et al demonstrated that human volar fibroblasts could also convert non-volar to volar keratinocytes in a SCID mouse model[2]. We ourselves have performed similar assays where we add mouse keratinocytes either alone or plus inductive fibroblasts and we can show that fibroblasts direct the development of hair growth. These results provide in vivo evidence on how fibroblasts can change epidermal function and control skin identity.

In the course of these studies we have enrolled 11 participants who have had sole/foot biopsies (NA_00033375). Of 11 biopsies, only a single one had a possible infection which was successfully treated with antibiotics. Otherwise there were no adverse events. Therefore we predict a similar safety profile for the currently proposed study.

Phase One - Proposed therapeutic outline:

1. Biopsy palmo/plantar skin at the sole of the foot and the scalp (or other area with suitable non-volar skin) (note higher KRT9 in native tissue in Fig 4 and KRT9 induction in Fig 5)
2. Expand autologous palmo/plantar fibroblasts
3. Inject autologous fibroblasts into stump site (in the current proposal we will first test healthy participants and not amputees)
4. Monitor for conversion to ectopic palmo/plantar skin

Phase Two – Proposed therapeutic outline:

1. Biopsy palmo/plantar skin at the sole of the foot and the scalp (or other area with suitable non-volar skin) (note higher KRT9 in native tissue in Fig 4 and KRT9 induction in Fig 5)
2. Expand autologous palmo/plantar fibroblasts

3. Inject autologous fibroblasts into stump site (in the current proposal we will first test healthy participants and not amputees)
4. Introduce intermittent dosing regimen of autologous fibroblasts (multiple injections vs. single injection) or RIMSO-50 injection (50% DMSO), and superficial wounding with a curette in a subset of subjects.
5. Monitor for conversion to ectopic palmo/plantar skin.

